Waitlist Control Arm: The BIPOC trans women randomized into the control arm (n=20) will initially receive only standard of care derived from the existing community-based services of TSoCP and Fair Michigan during the 12-week period following randomization. Standard of care services include:

- 1. One-time Emergency Assistance: Participants will receive up to \$250 in emergency assistance funds to pay for immediate needs (e.g., housing, bills, food).
- 2. Linkage to Legal Gender Affirmation Support: All participants will have access to legal name/gender marker change through Fair Michigan.

Additionally, after the RCT follow-up period is complete (i.e., after completion of two follow-up surveys occurring at 12 and 24 weeks after baseline survey completion), waitlist control participants will be offered delayed access to the same *Secure* intervention that is provided

immediately to intervention arm participants. The *Secure* program components are described below.

Experimental Secure Intervention (12 weeks): The BIPOC trans women randomized into the intervention arm (n=20) will be enrolled in the 12-week Secure program after randomization, in addition to the standard of care services described above. The Secure program includes the four following components:

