- 1. 12 weekly Economic Empowerment (EE) and HIV Risk Reduction (HIVRR) Educational Sessions lasting 2 hours each and will be conducted in-person with approximately 8-10 participants. Session topics will focus on income acquisition assistance through skill development and goal setting relating to job-seeking (i.e., resumes, job application, interviewing), income generation through micro-business (i.e., self-employment, entrepreneurship, accessing clients, making a profit), and financial literacy (i.e., budgeting, managing credit). To address the relationship between economic vulnerability and HIV risk, session topics will also focus on knowledge and uptake of biomedical HIV prevention and treatment strategies (i.e., use of PrEP/ART) with particular attention to discussion of participants' financial constraints and trade-offs to protecting against HIV, and how safer income generation can be leveraged to reduce their risk of HIV transmission or acquisition (i.e., paying for travel to PrEP/ART clinics, acquiring higherpaying employment or health insurance, or refusing condomless sex work). Peer health educators (PHEs) will co-facilitate the interactive sessions, including role-play, discussions, games, and demonstrations. Each session will prioritize gender-affirming principles of social cohesion, mutual support, and identify affirmation.
- 2. Employment-Focused Mentorship where participants will meet with an employment-focused mentor weekly (~30 minutes/week) to assist her in acquiring or maintaining employment, initiating or expanding self-led income generation, or navigating financial decisions, including planning for use of their study-provided microgrants (see below). With the help of our team, we will identify approximately 8 mentors. Mentors will be offered an honorarium of \$450 per mentee.
- 3. Weekly Job Postings where study team members will collate three social media announcements each week (i.e., Instagram, Facebook) with job openings in the greater Detroit metropolitan area.

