VI-4.2 Exploratory analyses. To fulfill our secondary goal of generating preliminary effects of the intervention on the primary HIV serostatus-neutral HIV prevention and care engagement outcome, proportions of the outcome will be plotted by group over time to describe overall patterns of change across time in the *Secure* intervention group and the control group. Hypothesis testing will be de-emphasized in line with NIH¹⁵² and research methods literature cautions^{153,154} regarding the instability of inferential results from small-scale pilot studies. With that caveat, we anticipate that following the *Secure* intervention, intervention participants will exhibit higher odds of the HIV prevention and care outcome relative to control group participants in a time-averaged comparison of the post-baseline intervention and control groups' outcome proportions. This exploratory comparison will be performed at alpha=.05 in a generalized linear mixed model (GLMM) suitable for this binary outcome. Repeated observations from each participant will be the unit of analysis. Alpha will be set at 5% for this exploratory analysis.

VI-4.3 Power analyses. Although the main purpose of this study is to determine preliminary feasibility and acceptability and to visualize changes in outcomes and mechanisms of change over time rather than to perform formal hypothesis tests, we conducted several power analyses using NCSS PASS 21 156 to supply additional information. Assuming power=.80, α =.05, and N=32 participants available at the last follow-up, we computed confidence interval widths for a) proportions for binary variables and b) means for continuous variables measuring feasibility and acceptability. For example, for the study enrollment proportion, assuming α =.05, power=.80, and

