the 80% enrollment benchmark, the width of the confidence interval for single proportions is 29.8% (standardized distance to the limit: .40). For continuous variables, the distance from the mean to the confidence limit is .36. For mixed models proposed to explore group differences in outcomes, the minimum detectable proportion increase in HIV care and prevention ranged from 33.7% to 42.8% (standardized effect size h=.75-.92; odds ratios=4.94-7.56). Taken collectively, this study is powered to detect small to medium distances to confidence limits for descriptive statistics to assess feasibility and acceptability (primary goal) and large effects for preliminary effectiveness effects (secondary goal), though, as noted above, formal hypothesis testing will not be the focus of this pilot study.

V. Study Procedures

VII-1. COVID-19 Safety

The group session element of the *Secure* intervention is designed for in-person delivery while the mentorship component and study assessments may take place in-person or remotely. While the study team has successfully administered remote, at-home alternatives among trans women of color, previous experience in Detroit has demonstrated the strong preference for in-person activities among community members when possible. If levels of COVID-19 risk and community spread increase to the point that in-person group sessions are not safe, we will submit an amendment with virtual intervention procedures. All U-M affiliated study team members will complete the Environmental Health Services course entitled, "Working Safely at U-M" (EHS_OHS_COVIDW) and will be provided appropriate personal protection equipment when facilitating any in-person study activity (i.e., sterile single use masks). Partnered organizational sites where in-person study activities will be held (i.e., Ruth Ellis Center) have their own COVID-19 risk reduction procedures that are in accordance with city and state health department quidelines.

VII-2. Recruitment

We will employ a multi-pronged outreach strategy to recruit BIPOC trans women including 1) Online recruitment: Banner ads and posts will be placed on social media platforms used by trans women of color (Facebook, Instagram); 2) Print Ads: Flyers will be placed in healthcare and social service agencies in Detroit; 3) Outreach: Our study research associate (RA) will conduct outreach in areas where BIPOC trans women congregate in Detroit. (See "Recruitment Materials" Appendices.)

VII-3. Eligibility Screening

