VII-4.2 Baseline Survey: After consenting to participate, potential participants will be asked to complete an online Qualtrics programmed baseline survey. (See "Baseline Survey" Appendix.) The survey should take approximately 40 minutes to complete and will be connected to their assigned Study ID. If they are in-person with the study team member at Ruth Ellis, they may complete the survey on the study team laptop or tablet; if remote they will be sent a link via email and/or text message to complete on their personal device. If a participant requests to complete the survey at another time during an in-person study visit or exits out of the survey remotely before completion, study team members will attempt contact via phone call, email, or text to remind about completing the survey and provide their unique Qualtrics survey link if they are no longer able to locate it. In order to receive their incentive, at the end of the Qualtrics survey, participants will be asked to provide their name, mailing address, email address, and social security number (required for incentive reconciliation for tax purposes due to the amount of funds provided over the study period). An IRB approved study team member will securely store participants' social security number in a restricted Dropbox folder. (For specific incentive amount, see Section VII-8. Participant Incentives and Other Funds Provided.)

VII-4.4 Randomization: After all previous enrollment activities are completed, participants will be randomized in a 1:1 ratio into *Secure* intervention or the TSoCP/Fair Michigan standard of care waitlist control condition using a computerized secure and fraud-resistant procedure used in our team's prior studies. Assignment will occur until there is sufficient enrollment to form a group. A member of the study team will contact the participant to them know whether they are in the immediate intervention arm or the waitlist control arm. (See "Randomization Survey" Appendix.)

VII-5. Intervention Arm Procedures

During the approximately 12-week intervention period, participants who are randomized to the intervention arm will receive the Secure program components (in-person group sessions, individual mentorship, microgrant funds, and weekly job announcements), in addition to standard of care services (one-time emergency assistance funds, referral to legal gender affirmation services), as described below.

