VII-5.1 In-Person Group Sessions. When planning group session attendance, the study team will track enrolled participants newly randomized to the intervention arm. Once a sufficient number of intervention arm participants have been amassed, a study team member will assign them into a cohort. They will be contacted by U-M study staff over the phone, email, or text message to coordinate their participation in the group session content of *Secure*. Participants who state they are no longer able to commit to the group session series will be put back into the queue to be possibly included in a later cohort. Otherwise, participants will be reminded about each weekly in-person group session two days before and the morning of via text message. From these point on, those participants will have their weekly group session together once a week at the Ruth Ellis Center.

There are 12 group sessions total that will be completed over approximately a 12-week period. (See "Group Sessions" Appendix for group session content.) Ideally each group will include 10-

12 participants, with a minimum of 4 participants and a maximum of 14 participants. The group content focuses on micro-business development, entrepreneurship, financial literacy, and HIV/STI prevention and care. The group sessions will be facilitated by two BIPOC trans women that are a part of the study implementation team.

Secure group sessions will occur in a private room. Members of the study team will explain the confidentiality expectations of the group. Participants will be required to agree not disclose information about any other participant attending to anyone outside of the group including that they are participating in the Secure study. Participants will be allowed to join the group late. The room where the group will take place will include free food and non-alcoholic beverages for those in attendance. The two group facilitators present will explain that they reserve the right to ask any participant to leave during the session if they are being overly disruptive to the content delivery. Participants who miss one or more of their 12 weekly group sessions will not be offered make-up sessions. Participant attendance and any reason(s) given for absences will be documented.

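### Secure is delivered in fixed groups in one arm only, but the exploratory GLMM and the detectable effects make no visible allowance for group correlation; if that correlation is above zero, precision is overstated

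*Combined protocol and SAP*

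**What the plan says.** Allocation is individual: under VII-4.4, "participants will be randomized in a 1:1 ratio into" the two conditions. The intervention arm has 20 people (VI-2). Its educational sessions are "conducted in-person with approximately 8-10 participants" according to VI-2. VII-5.1 gives a different target, ideally 10-12, and permits 4 to 14. Once a cohort is formed, "those participants will have their weekly group session together once a week at the Ruth Ellis Center", for 12 sessions with two facilitators. Under VII-5.2 a mentor may also serve more than one member of a cohort. During the comparison period the waitlist arm receives only the standard services and is not grouped.

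VI-4.2 specifies a time-averaged, post-baseline comparison in a GLMM for a binary outcome. On dependence it says "Repeated observations from each participant will be the unit of analysis", and on error rate "Alpha will be set at 5% for this exploratory analysis". VI-4.3 assumes 80% power and "N=32 participants available at the last follow-up". It then reports that "the minimum detectable proportion increase in HIV care and prevention ranged from 33.7% to 42.8" percent, with h=.75-.92 and odds ratios 4.94-7.56, and concludes that the study is powered for large effects on its secondary goal. No cohort, facilitator or mentor term, ICC or design effect appears in either section.

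**The concern.** This is a partially nested design: people are randomized singly, but one arm is treated in groups. Sessions rely on discussion, role-play and mutual support, so influence between group members is part of how the programme is meant to work. Outcomes within a cohort may therefore be correlated, while control outcomes have no such source of correlation. A model with only a participant-level effect would then understate the variance of the intervention-arm estimate.

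What is at stake is the width of the GLMM interval, the reading of its p-value, and whether the detectable effects in VI-4.3 really correspond to 80% power. The pilot is also meant to prepare a larger trial, where a nested structure that goes unnoticed would cost more.

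**Working it through.** **Inputs from the documents.** 20 randomized per arm; 32 analysed at last follow-up, taken as 16 per arm; two post-baseline surveys; alpha .05, taken as two-sided because the documents do not say; power .80; detectable h=.75-.92; group sizes 4 to 14.

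**Assumed.** Group ICC of 0 to .10; equal arms and variances; normal approximation. The ICC applies to each participant's time-averaged result.

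**Number of groups.** 20/10 = 2 and 20/8 = 2.5 at the VI-2 target; 20/4 = 5 at the minimum size.

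**The plan's own figures.** Two other VI-4.3 figures reproduce: the Clopper-Pearson width for 80% at n=32 is 29.8%, and t/√32 = .36. The detectable-effect range cannot be reproduced uniquely, because the control proportion and within-person correlation are not stated. It can be checked for consistency with a model that has participant-level correlation only. From h = (1.96+0.84)·√(2/n_eff):

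- h=.75 needs n_eff = 2·(2.80/.75)² ≈ 27.9 per arm.
- h=.92 needs n_eff = 2·(2.80/.92)² ≈ 18.5 per arm.

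Sixteen people with two surveys each give n_eff = 32/(1+ρ), so ρ ≈ .15 and ρ ≈ .73. Both are possible within-person correlations, so the range fits with no group allowance. That is inference from fit and from the described model; the documents do not show it directly.

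**Effect of grouping in one arm.** With m analysed per group, DE = 1+(m−1)·ICC in the intervention arm and 1 in the control arm. The variance of the difference is multiplied by v = (DE+1)/2. Detectable h is multiplied by √v, and power at the stated effect is Φ(2.80/√v − 1.96). For example, with m=8 and ICC .05: DE = 1+7(.05) = 1.35, v = 1.175, √v = 1.084, h = .81-1.00, and power = Φ(2.58−1.96) = 73%.

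| m | ICC | DE | √v | detectable h | power at stated effect |
|---|---|---|---|---|---|
| any | 0 | 1.00 | 1.000 | .75-.92 | 80% |
| 8 | .01 | 1.07 | 1.017 | .76-.94 | 79% |
| 8 | .05 | 1.35 | 1.084 | .81-1.00 | 73% |
| 8 | .10 | 1.70 | 1.162 | .87-1.07 | 67% |
| 4 | .01 | 1.03 | 1.007 | .76-.93 | 79% |
| 4 | .05 | 1.15 | 1.037 | .78-.95 | 77% |
| 4 | .10 | 1.30 | 1.072 | .80-.99 | 74% |

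**Rejection rate.** 2(1−Φ(1.96/√v)) gives 7.1% and 9.2% for groups of 8 at ICC .05 and .10. These rates need a particular null: groups have real effects that average to zero.

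The table takes no penalty for the very small number of groups and ignores shared mentors. Either would worsen the figures.

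**The case against.** The strongest reply is that the plan already limits this inference. VI-3 disclaims formal outcome testing and effect-size estimation, VI-4.2 de-emphasizes hypothesis tests, VI-4.3 offers its power figures as extra information, and no benchmark depends on the p-value. Amendment XI-4 reports that enrollment and all surveys are complete, so restated power cannot change the design. All of this stands and limits the impact. It does not remove the alpha=.05 comparison in VI-4.2 or the statement in VI-4.3 about what the study is powered to detect. If those figures are given, the assumption behind them should be given too.

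A second reply is that about two groups cannot support an estimate of between-group variance. That is correct, and adding a cohort random effect would not repair the inference. It is a reason to use assumed ICC values, not to leave a value of zero unstated.

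A reader might infer that the test simply does not hold its 5% level. The documents do not support that. Allocation is individual, and cohorts are formed afterwards in one arm. If Secure affects nobody, delivery creates no group correlation, and randomization protects the test. A reader might also infer that the feasibility intervals are too narrow. The illustrated proportion interval concerns enrollment, which precedes grouping, so it is unaffected.

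**Conclusion.** The point holds conditionally. The documents establish fixed cohorts in one arm, ungrouped controls, and an analysis description with no group allowance. For any positive intervention-arm ICC, the GLMM interval is too short and h=.75-.92 is optimistic. The size depends on an ICC that the documents do not give and on group sizes that may range from 4 to 14. For groups of 4 to 8 with 16 analysed per arm, the loss is negligible at ICC .01. At .05 to .10, detectable h rises by about 4% to 16% and power falls to between 77% and 67%. The absence of an allowance in VI-4.3 is inferred, because its inputs are not reported. The consequence is confined to the exploratory comparison.

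**What to change.** - **VI-4.3:** label h=.75-.92 as assuming zero group correlation. Add detectable effects for ICC 0 to .10 and group sizes 4 to 10, using an intervention-arm design effect of 1+(m−1)×ICC. Match the number analysed to the group size: two groups of 10 mean 20 per arm, not 16. Report the control proportion and within-person correlation used.
- **VI-4.2:** keep the participant random effect and carry the cohort ID into the analysis file. Report the effect interval a second time with intervention-arm variance inflated for assumed ICC .05 and .10. State that the p-value assumes no group correlation.

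The cost is some SAP wording and a short plug-in calculation, with no new data collection: VII-5.1 already has staff assign cohorts and document attendance. The downside is slightly less favourable figures that rest on an assumed ICC.

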In alignment with the Ending the HIV Epidemic (EHE) plan and NIH priority areas for reducing HIV incidence, ^{24,25} the goal of this study is to develop and pilot test an HIV statusneutral, gender-affirming microeconomic intervention to decrease economic vulnerability and thereby promote HIV prevention (HIV testing and PrEP use) and care (viral suppression) among BIPOC trans women in Detroit, Michigan, an EHE priority jurisdiction. ^{26,27} The gender-affirming microeconomic intervention named, "Strengthening Community Responses to Economic Vulnerability among Trans Women (Secure)" builds on our community's existing usual care (UC) microeconomic intervention of: (1) an emergency unconditional cash grant (averaging \$200)²⁰ and (2) peer and legal support to obtain legal gender affirmation (i.e., legal name and gender markers on identification documents). ²⁶⁻²⁸ The 12-week microeconomic intervention (Secure) will include our community partners' UC plus: (1) weekly educational sessions on economic empowerment (i.e., job acquisition, income generation through micro-business, and financial literacy) and HIV prevention and care; (2) employment-focused mentoring; (3) weekly social media posts of job openings in Detroit; and (4) an unconditional grant (\$1,200) for use towards acquiring self-led or formal employment. The specific aims are to:

III-1. Aim 1: Assess the feasibility of the *Secure* intervention to be implemented in the Detroit transgender community setting.

III-2. Aim 2: Evaluate the acceptability of the *Secure* intervention to improve HIV prevention and care continua outcomes.

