VII-6.3 Waitlist Control *Secure* Content Access: After the 12-week period when an active intervention arm cohort completes the *Secure* program content (i.e., completion of group session 12 when participants graduate from the program), both the intervention and waitlist control conditions will enter into a 3-month follow-up period. After the waitlist control arm participants complete a follow-up survey at the end of the 3-month follow-up period, they will be offered the opportunity to receive the *Secure* program. If interested, waitlist control participants will be placed into a group cohort and will follow the same study procedures outlined for intervention arm participants in section VII-5 over another approximately 12-week period.

VII-7. Follow Up Assessments and Additional Intervention Fidelity Documentation

VII-7.1 Follow-up Survey Assessments: After completing all the intervention or waitlist control study activities, participants will receive an immediate post-program follow-up survey following the completion of the intervention arm content (i.e., completion of group session), approximately 3-months from when they completed the baseline assessment. Then three months after post-program follow-up survey, both conditions will complete a final 3-month follow-up survey. The post-program and 3-month follow-up assessments will consist of online Qualtrics programmed surveys and disseminated over email and text message for remote completion. Survey hyperlinks will be unique for each participant with embedded metadata containing their Study ID number, and will not include personally identifying information. (See "Follow Up Survey" Appendix.)

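### The stated precision uses N=32 for measures it does not fit: acceptability and other participant-level Secure measures (about 20 people), and the enrollment proportion (people screened or eligible)

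*Combined protocol and SAP*

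**What the plan says.** Section VI-4.3 bases its precision figures on "N=32 participants available at the last follow-up, we computed confidence interval widths". It applies them to proportions and to "means for continuous variables measuring feasibility and acceptability". The worked example is enrollment, with an assumed rate of 80%; the plan reports for it that "the width of the confidence interval for single proportions is 29.8% (standardized distance to the limit: .40". Its companion figure, in SD units, is that "the distance from the mean to the confidence limit is .36". The section concludes that "this study is powered to detect small to medium distances to confidence limits for descriptive statistics to assess feasibility and acceptability (primary goal".

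Other sections show who has received what by that time:

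- **Specific Aims.** Aim 2 is about Secure itself and opens with "Evaluate the acceptability of the". Forty women are randomized.
- **VI-2 and VII-4.4.** Allocation is 1:1, with 20 per arm. Only the intervention arm starts Secure after randomization.
- **VII-6.3.** Waitlist access to Secure comes later: "After the waitlist control arm participants complete a follow-up survey at the end of the 3-month follow-up period, they will be offered the opportunity".
- **XI-4 (Ame00160383).** Waitlist group sessions are cut from 12 to 5, and the waitlist exit interview is removed.
- **VI-3, VII-5.1 and VII-7.2.** Acceptability data are a feedback form after each group session, facilitator feedback, and an exit interview within a month of the last session.

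**The concern.** The plan gives one N for every feasibility and acceptability measure. At the last follow-up, half of the randomized sample has had no Secure session, mentor or microgrant and so has nothing to rate. A reader who takes the .36 or the 29.8 points as the precision for acceptability would think it better than a 20-person arm can give.

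The enrollment example has a different fault. Everyone present at the last follow-up enrolled, so the enrollment proportion among those 32 is 100% by construction. An 80% enrollment rate needs a denominator of people approached, screened or eligible.

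At stake is how much uncertainty is reported for part of the primary goal, and how much of it carries into planning the efficacy trial named in the Specific Aims.

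**Working it through.** **Inputs.** Two-sided 95% intervals (alpha .05), p = .80 and N = 32, from VI-4.3. 40 randomized, from the Specific Aims; 20 per arm, from VI-2. Since 32/40 = 80%, and one arm holds only 20, the 32 must span both arms. The plan does not say this outright.

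**Formulas.**
- Proportion: Clopper-Pearson limits, lower = Beta(.025; x, n−x+1) and upper = Beta(.975; x+1, n−x), with x = .8n (fractional where .8n is not whole).
- Standardized distance: h = 2·arcsin√.80 − 2·arcsin√(lower limit).
- Mean: t(.975, n−1)/√n, in SD units.

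**Step 1: the plan's own figures, n = 32.**
- Limits 62.1% to 92.0%; width 29.8 points (stated 29.8).
- h = .398 (stated .40).
- Mean: 2.0395/√32 = .3605 (stated .36).

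All three reproduce, so N = 32 was the number used. The stated power of .80 plays no part in them.

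**Step 2: participants who have received Secure.**

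| n | 95% limits at 80% | Width (points) | h | Mean distance (SD) |
|---|---|---|---|---|
| 32 (as stated) | 62.1% to 92.0% | 29.8 | .40 | .36 |
| 20 (whole intervention arm) | 56.3% to 94.3% | 37.9 | .52 | 2.0930/√20 = .47 |
| 16 (sensitivity: 20% of the arm gives no data) | 53.0% to 95.4% | 42.4 | .58 | 2.1314/√16 = .53 |

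At n = 20 the proportion interval is 37.9/29.8 = 1.27 times as wide as stated, and the mean distance is .468/.3605 = 1.30 times the stated one. At n = 16 the ratios are 1.42 and 1.48. The n = 16 row uses x = 12.8, which cannot be observed. The nearest real results are 12/16 (48% to 93%) and 13/16 (54% to 96%).

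**Step 3: repeated session forms.** With 20 people and 12 sessions there are at most 20 × 12 = 240 forms. With within-person correlation r, the effective n of a mean over all forms is 240/(1 + 11r). This assumes full attendance and ignores cohort clustering, which would lower it. The documents give no r; over an assumed range:
- r = .2: 240/3.2 = 75
- r = .5: 240/6.5 = 37
- r = .75: 240/9.25 = 26

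This equals 32 when 1 + 11r = 240/32 = 7.5, that is r = .59. Below that a pooled-form mean does better than N = 32; above it, worse.

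**Step 4: enrollment.** The denominator is not given. If the 40 enrolled are 80% of those eligible, it is 40/.80 = 50: limits 66.3% to 90.0%, width 23.7 points. At the smallest denominator that could yield 40 enrolled, n = 40, the width at 80% is 26.6 points. So at 80% any feasible denominator gives a narrower interval than the stated 29.8.

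**The case against.** Several counter-arguments have force.

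- **The change in wording is small.** On the usual .2/.5/.8 scale, .47 and .52 are medium, and the plan already says small to medium. This stands: at n = 20 the correction is from small to medium to about medium, no further.
- **n = 16 is not the design value.** It carries 80% retention at the 24-week survey, assumed equal by arm, over to acceptability. Session forms and exit interviews are collected earlier, and loss at week 24 does not remove forms already completed. This stands, so 16 is only a sensitivity case.
- **Pooled session forms may match or beat 32.** This stands, subject to the unknown correlation. But VI-4.3 counts participants at the last follow-up, not forms, so it does not rescue the stated basis.
- **The original design would have produced waitlist ratings.** VII-6.3 and VII-7.2 put waitlist participants who opt in through the same procedures, with an exit interview. This is true, but those data come after the last follow-up that defines N = 32, and Ame00160383 then limited them to 5 sessions with no exit interview.

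A reader might go further and infer that the principal aim rests on precision for the wrong group. The documents do not support that. The listed benchmarks are point criteria, the analysis in VI-4.1 is descriptive, and VI-4.3 offers its figures only as supplementary information. No decision rule uses a confidence interval.

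A reader might also infer that no acceptability benchmark exists, because VI-4.1 says one will be evaluated and the body states none. The appendix surveys were not available for this review, so the supportable request is to cite where it is set. Likewise, the recruitment target of at least 5-6 per month reads naturally as a floor of 5, and its ambiguity is a wording point.

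**Conclusion.** The concern holds in a limited form. The arithmetic in VI-4.3 is correct for n = 32, and that N is reasonable for measures taken in both arms, such as survey retention and missing data. It is the wrong denominator for two things:

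- **Participant-level measures that need exposure to Secure.** With 20 people the intervals are about 27% wider for a proportion at 80% and 30% wider for a mean than stated, and the distances are about medium. This assumes that all 20 give data; if 20% do not, the excess is 42% and 48%.
- **The enrollment proportion.** The stated interval is too wide rather than too narrow. By how much depends on the number screened or eligible, which the plan does not give.

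No failure of the retention or missing-data benchmarks is implied. Means pooled over session forms are a separate case and could be more or less precise than stated. The point merits correction because the precision statement concerns the primary goal and the correction is cheap.

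**What to change.** 1. In VI-4.3, give precision by measure, each with its own denominator. Keep the both-arm N for measures taken in both arms.
2. For participant-level Secure measures, state n = 20: 56.3% to 94.3% at 80%, width 37.9 points, h .52, mean distance .47 SD. Show n = 16 (42.4 points, .53 SD) only as a sensitivity case. Describe these distances as about medium.
3. Note that means over repeated session forms have a different effective n that depends on within-person correlation, and show the number of forms.
4. Recompute the enrollment interval on the actual number screened or eligible, and name that denominator. The 80% enrollment benchmark should also appear in the Specific Aims list, which omits it.
5. Report the 5-session waitlist data separately from the 12-session intervention-arm data.
6. As secondary wording, cite where the acceptability benchmark is set or report acceptability descriptively, and give recruitment a single floor.

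Cost: recalculation and rewording only. Ame00160383 reports enrollment and follow-up complete, so observed denominators can be used. The downside is a less favourable precision statement for acceptability; the enrollment statement is likely to improve.
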